5.4. Per Protocol (PP) Analysis Set

The Per Protocol analysis set will include all subjects in the FAS Analysis Set who do not have major protocol violations that would affect the evaluation of the primary efficacy endpoints. The PP analysis set will be used only for the supplementary analysis of co-primary endpoints. Subjects will be analyzed according to their randomized treatment.

Subject assignments to the PP Analysis Set will be determined after blinded data review to assess major protocol deviations necessitating exclusion from the PP Analysis Set prior to any unblinding of treatments for formal statistical analysis. Major protocol deviations are defined in Section 7.3.

5.5. Pharmacokinetic (PK) Analysis Set

The PK Analysis Set will include all subjects in the Safety Analysis Set who have at least one quantifiable postdose PK sample available and who do not have protocol deviations or events with the potential to affect PK concentrations. The PK Analysis Set will be used for all PK analyses and listings of PK concentration data.

6. GENERAL ASPECTS FOR STATISTICAL ANALYSIS

6.1. General Methods

The following conventions will be utilized in the analyses:

- The final statistical analysis will not be performed until all the reportable data have been collected, queries answered, and the database locked.
- All relevant individual subject data will be provided in data listings sorted by treatment arm and subject number. The following treatment group labels will be used: "Placebo", "etokimab Q8W", and "etokimab Q4W". Where subjects who were not randomized are included in listings, the treatment arm will be indicated as "Not Assigned" or "Not Randomized".
- Tabulations will be produced for appropriate demographic, baseline, efficacy and safety parameters. All tabular summaries will be presented by treatment arm as indicated above. A total column may be included under "All Subjects" where necessary or appropriate.
- In general, continuous variables will be summarized by descriptive statistics including the number of observations (n), mean, standard deviation (SD) or standard error (SE), median, minimum (min), and maximum (max); the lower (Q₁) and upper quartile (Q₃) may be included in some summaries if deemed necessary or important. The same number of decimal places as the raw data will be presented when reporting min and max, 1 more decimal place than in the raw data will be presented when reporting mean, median, lower and upper quartiles and 2 more decimal places than in the raw data will be presented when reporting SD or SE.
- Categorical data will be summarized using the number of observations (n), frequency, and percentage of subjects in the relevant analysis set and treatment group falling within each category.
- Unless otherwise specified, where there are multiple measurements at a post-baseline visit or time of assessment, the value closest to the target date within the specified window for the assessment visit will be used for analysis.
- For numerical variables, change from baseline will be calculated as the value of interest at the time of measurement minus the corresponding baseline value.
- All statistical tests will be two-sided; unless otherwise indicated; two-sided p-values < 0.05 will be regarded as statistically significant, and confidence intervals (CI) will be 2-sided and have 95% confidence level.
- All subject data will be included in listings.
- Data analyses will be conducted using validated computer software (e.g. SAS[®] Version 9.4 or higher).
- Adverse events will be coded using the most recent MedDRA version 21.0 or higher.
- Concomitant medications will be coded using the most recent version of World Health Organization (WHO) -DDE version March 2018 or later.
- In this SAP, we will designate the treatment arms as Placebo, etokimab Q4W, and etokimab Q8W. In data presentations, etokimab Q4W will be in the 1st column, etokimab Q8W in the 2nd column, and the Placebo group in the 3rd column.

6.2. Key Definitions

6.2.1. Baseline

Unless otherwise specified, "baseline" is defined as the last observed value of the parameter of interest prior to the first intake of study medication (this includes unscheduled visits). Definitions of baseline for specific efficacy and/or safety parameters are provided in relevant sections where those parameters are defined and their analysis methods described.

For numerical variables, change from baseline will be calculated as the value of interest at the time of measurement minus the corresponding baseline value.

6.2.2. Study Day

The first dose date is defined as the date the first dose of study medication was received after the subject was randomized. Study medication is expected to be administered in the pharmacy on Study Day 1, the randomization visit date, also the same as the Visit 2 date. In the protocol, reference to Week 0 may be regarded as Study Day 1. Study days used in the subject listings are calculated from Study Day 1.

For Study days on or after the date of treatment start, Study Day will be calculated as:

```
Study day = Assessment date - First dose date + 1
```

For study days prior to dosing, Study Day will be calculated as:

```
Study day = Assessment date – First dose date
```

There is no Study Day 0.

6.2.3. Study Periods

This study has 3 periods: a 4-week screening period (maximum days 31 days), with a minimum MFNS run-in of 20 days prior to the administration of study medication on Day 1; a 16-week treatment period (Week 0 to Week 16); and an 8-week safety follow-up period.

Period	Start	End
Screening/Baseline	Visit 1 date	Day 1 (Visit 2) date - 1
Treatment Period	Day 1 (Visit 2 date)	Visit 7/EOT date - 1
Safety Follow-up	Visit 7/EOT date	Visit 9/EOS date

Day 1 is Week 0.

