*UPSIT only. Lund-MacKay score is not assessed at Week 8.

**UPSIT and Lund-MacKay scores do allow gaps between analysis visits.

Table 2f: Visit Windows for Assigning PW Visits to an Analysis Visit for EQ-VAS, Nocturnal Awakenings, and NPIF

Study Period	Visit	Target Day*	Window for Reassignment to Scheduled Visit
Baseline	Baseline	1	≤ 1
Treatment Period	Week 1	5	2-7
	Week 2	11	8-14
	Week 3	18	15-21
	Week 4	25	22-28
		•••	
	Week 16/EOT	102	99-105
Safety Follow-up Period	Week 20	130	127-133
	Week 24/EOS/ETV**	158	155-161

*Except for Week 1, Target Day for the rest weekly analysis visits is the mid-week day.

**The last observation in the time window will be used. [This is an exception from the rule regarding closest to target.]

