8. EFFICACY

The primary efficacy objective of this study is a comparison of each of two dosing regimens of etokimab with placebo in the treatment of subjects with CRSwNP following a 16-week treatment period (change from baseline using co-primary endpoints). Two co-primary efficacy endpoints will be analyzed.

The analysis of the primary and secondary efficacy parameters will be performed on the FAS, unless otherwise noted. The primary and secondary efficacy analyses will be repeated on the PP analysis set if there are substantial differences between the makeup of the FAS and the PP Analysis Set, in order to assess the impact of major protocol deviations on the key inference.

All primary and secondary efficacy variables will be analyzed for data obtained for the Treatment Period.

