8.1.1. Nasal Endoscopy

Nasal endoscopy is performed acc ording to the schedule of assessments in Table 1, on Day 1, Week 4, Week 8, Week 12, Week 16 and Week 24. Each nostril is scored on a scale of 0 to 4, and hence the total NPS value at each visit is between 0 and 8. For each nostril, a score of 0 means no polyps, while a score of 4 means the presence of polyps causing complete obstruction of the inferior nasal cavity. The NPS value at the screening visit is used to determine qualification for enrollment in the study. The NPS score at Week 24 is for safety follow-up.

If a subject's NPS image is initially evaluated as unreadable, the subject may be asked for a repeat endoscopy. If the original image is taken during the screening period, the subject will be asked to repeat endoscopy. If the original image is during post-randomization, the endoscopy will not be repeated with the exception of the Week 8 and Week 16 images. If the images taken for the Week 8 or Week 16 visits are not readable, every attempt should be made to repeat the procedure as close to the original visit window and the re-taken image will be used for analysis. For analysis purposes, baseline endoscopic score (NPS value) will be defined as the total (left and right) NPS value reported at the last visit on or prior to the first dose date (Day 1). Total NPS values will also

be obtained at each visit during Treatment Period (Week 4, 8, 12 and 16), and at the end of the Safety Followup Period (Week 24).

A listing of nasal endoscopy performance, nasal polyp scores, and change from baseline scores will be provided per visit per subject for the Full Analysis set.

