8.3.2. Lund-Mackay Scores

Computed tomography of the sinuses is performed at the clinic on Day 1 and at EOT (Week 16). The Day 1 CT is collected prior to dosing on Day 1. As indicated in the protocol, if necessary, the Day 1 CT can be collected prior to Day 1, however all efforts should be made to conduct CT after subject screening labs have been reviewed and it is determined that the subject is likely eligible for the study. CTs collected within 3 months prior to randomization (Day 1) can be used in lieu of a new Day 1 CT if the necessary imaging requirements are present.

The Lund-Mackay (L-M) scoring system is based on localization with points given for degree of opacification: 0 = normal, 1 = partial opacification, 2 = total opacification. These points are then applied to the maxillary, anterior ethmoid, posterior ethmoid, sphenoid, and frontal sinus on each side. The osteomeatal complex is graded as 0 = not occluded, or 2 = occluded deriving a maximum score of 12 per side (Lund and MacKay, 1993). For patients in whom the osteomeatal complex (OC) is missing (because of a previous surgery) the reader should consider the location of the former OC and provide a scoring (as if the OC was there). An aplastic

(absent) frontal sinus receives a score of 0. Thus, a combined L-M score of up to 24 is possible. The table below summarizes the scoring system:

Sinus	Right sinus	Left sinus
Frontal	0, 1, 2	0, 1, 2
Anterior ethmoids	0, 1, 2	0, 1, 2
Posterior ethmoids	0, 1, 2	0, 1, 2
Maxillary	0, 1, 2	0, 1, 2
Sphenoid	0, 1, 2	0, 1, 2
Ostiomeatal complex	0, 2	0, 2
Total score for each side	0-12	0-12

For the sinuses: 0=normal; 1=partial opacification; 2=total opacification.

For the ostiomeatal complex: 0=not occluded; 2=occluded

The L-M total score is obtained by summing the scores for the right and left sinuses. For simplicity, we will refer to the total score as the L-M score. Higher values for the L-M scores indicate more opacification.

Baseline L-M score will be defined as the L-M score obtained on Day 1, or the last available L-M score prior to treatment on Day 1. The L-M score at Week 16/EOT will be defined as the last value available during the treatment period.

Summary statistics will include n, mean, standard deviation, median, minimum, and maximum, and the percent change from baseline. A Wilcoxon signed ranks test p-value for the within treatment group percent change from baseline will be displayed.

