The etokimab dose groups will be compared to the Placebo group during the treatment period (up to Week 16) only. The values obtained between Week 17 and Week 24will not be included in the efficacy analysis, as follow-up is intended for safety only.

Statistical analysis of morning/evening NPIF during the treatment period will employ an MMRM, where the change from baseline in Weeks 4, 8, 12 and 16 AM (PM) NPIF values are modeled using the baseline value as a covariate; treatment (3 levels), stratification factor, treatment by stratification factor, categorical time (Weeks 4, 8, 12 and 16), and treatment by time interaction as fixed effect factors; and subject (the repeated measures) as random effect. The analysis is similar to that performed for the NPS and SNOT-22 scores.

The primary time point for the analysis of morning/evening NPIF is Week 16. The Week 16 least squares adjusted means from the MMRM will be used to perform pairwise comparisons of each etokimab dosing regimen with the Placebo group. An estimate of treatment difference and accompanying 95% confidence intervals will be produced from the model. It is expected that treatment with etokimab will lead to higher AM/PM NPIF values at Week 16 than obtained at baseline. A statistically significant difference (P<0.05) where the least squares means for the etokimab group is higher than for the Placebo group will be regarded as evidence of efficacy for etokimab compared to Placebo.

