10.2. Adverse Events

For the purpose of this study, an adverse event (AE) is any untoward medical occurrence (e.g., sign, symptom, disease, syndrome, intercurrent illness, clinically significant abnormal laboratory finding, injury, or accident) that emerges or worsens following initial administration of the study medication (eg., mometasone furoate nasal spray) and until the end of study participation. The untoward medical occurrence may not necessarily have a causal relationship to the administration of the investigational product. An AE can therefore be any unfavorable and/or unintended sign (including a clinically significant abnormal laboratory result), symptom, or disease temporally associated with the use of a medicinal (investigational) product, whether or not related to the medicinal (investigational) product.

A serious adverse event (SAE) is any untoward medical occurrence that at any dose: results in death, is life-threatening, requires hospitalization or causes prolongation of existing hospitalization.

A treatment-emergent AE (TEAE) is an AE that occurs or worsens in severity after any exposure to the investigational product (etokimab or placebo). If an AE starts between the screening visit and the randomization visit, and is ongoing at the time of treatment initiation, it may be deemed treatment emergent if it worsens in severity/severity. In that case, a separate event is to be recorded in the subject's eCRF indicating the worsened severity.

Section 6.3.4 of this SAP provides conventions for handling missing dates for AEs, for determining treatment emergence in the presence of missing data, and for assigning severity and treatment-relatedness in the presence of partial or missing start/stop AE dates.

All adverse events will be coded using MedDRA version 21.0 or higher. The TEAE reporting period begins with administration of the first dose of study medication on Day 1 and continues until the Visit 7 (Week 16 visit, or 28 days after the last dose of study medication). The Safety Follow-Up AE reporting period begins 29 after the last dose of study medication through completion of the Safety Follow-Up Period (Week 24 visit).

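### Three SAP time rules need correcting: the Treatment Period stops the day before the Week 16 visit, Table 2f's Weeks 16, 20 and 24 are really Weeks 15, 19 and 23, and visits after EOT are counted from last dose but read from first-dose tables

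*SAP*

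**What the plan says.** **Period dates.** The text of SAP 6.2.3 describes "a 16-week treatment period (Week 0 to Week 16". The table beneath it ends that period at "Visit 7/EOT date - 1" and starts Safety Follow-up on the Visit 7/EOT date itself. SAP 8 then states: "All primary and secondary efficacy variables will be analyzed for data obtained for the Treatment Period". SAP 8.1.1 says total NPS values will "be obtained at each visit during Treatment Period (Week 4, 8, 12 and 16", and SAP 8.3.2 says: "The L-M score at Week 16/EOT will be defined as the last value available during the treatment period". For adverse events, SAP 10.2 runs the treatment-emergent period to Visit 7, or 28 days after the last dose, and then says: "The Safety Follow-Up AE reporting period begins 29 after the last dose of study medication".

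**Weekly windows.** SAP 6.4 assigns diary data to analysis weeks counted from Day 1, Weeks 1 to 24. Table 2f prints Week 2 as Days 8–14, Week 3 as 15–21 and Week 4 as 22–28. It then skips to Week 16 as Days 99–105, Week 20 as 127–133 and Week 24 as 155–161. A footnote adds: "Except for Week 1, Target Day for the rest weekly analysis visits is the mid-week day". SAP 8.3.3 makes Week 16 the primary NPIF time point and says: "The values obtained between Week 17 and Week 24will not be included in the efficacy analysis". Section 6.4 and the title of Table 2f list the EQ-VAS among these diary data.

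**Visits after EOT.** SAP 6.4 first maps unscheduled, EOT and ET visits by study day from first dose. The next sentence maps unscheduled visits dated after the EOT visit, ET visits included, by days since last dose, and refers to the same tables.

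**The concern.** Each rule gives a different answer from the rest of the plan when applied as written.

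- **Period dates.** A programmer who flags study period by date would put the Week 16 NPS and SNOT-22 in Safety Follow-up, and SAP 8 would then drop them. The sinus CT is scheduled only at Day 1 and Week 16, so the date rule combined with SAP 8.3.2 leaves no post-baseline Lund-Mackay value. The only way out is to override SAP 6.2.3 without written authority.
- **Weekly windows.** The NPIF value reported for Week 16 would come from the wrong week, and the last full treatment week would be labelled as one that SAP 8.3.3 excludes.
- **Visits after EOT.** The tables' target days (29, 57, 85, 113, 141, 169) are study days from first dose. Entering them with days since last dose moves a follow-up record back to an on-treatment visit and removes it from its true window.

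**Working it through.** **1. Period dates.** Visit 7 is scheduled on Day 113 ± 5 (Schedule of Activities). The SAP 6.2.3 period end is the Visit 7 date minus 1.

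| Visit 7 | Treatment Period ends | Follow-up starts | Week 16 visit inside? |
|---|---|---|---|
| Day 108 | Day 107 | Day 108 | No |
| Day 113 | Day 112 | Day 113 | No |
| Day 118 | Day 117 | Day 118 | No |

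The visit can never fall inside the period. Against this, Tables 2a, 2b, 2d and 2e list Week 16 under the treatment period. SAP 8.1.1.2 models Weeks 4, 8, 12 and 16, and Protocol 4.1 places the Day 113 visit in the treatment period.

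For adverse events, with last dose on the Day 85 target, the treatment-emergent period ends on Day 85 + 28 = 113 and follow-up starts on Day 85 + 29 = 114. SAP 6.2.3 starts follow-up on Day 113, one day earlier.

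**2. Table 2f.** Week w covers Days 7(w−1)+1 to 7w, with mid-week target 7(w−1)+4. This reproduces the printed Weeks 2, 3 and 4 exactly: 8–14 (11), 15–21 (18), 22–28 (25). It does not reproduce the later rows.

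| Printed label | Printed window (target) | Week by the rule (last day ÷ 7) | Rule for that label |
|---|---|---|---|
| Week 16 | 99–105 (102) | 105/7 = 15 | 106–112 (109) |
| Week 20 | 127–133 (130) | 133/7 = 19 | 134–140 (137) |
| Week 24 | 155–161 (158) | 161/7 = 23 | 162–168 (165) |

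- Between the printed Week 4 and Week 16 lie Days 29–98, which hold (98 − 28)/7 = 10 blocks. Weeks 5 to 15 need 11.
- Calling the first week Week 0 does not help, because the rows then become Weeks 14, 18 and 22.
- The printed Week 16 window shares no day with Days 106–112. Counting on from the printed label, Days 106–112 are Week 17.
- Days 162–168 have no window.

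Scale name: the EQ-VAS is part of the EQ-5D (SAP 8.3.1.2). The schedule collects the EQ-5D at clinic visits, and QoL in Table 2a already covers it. The weekly diary scale is the rhinosinusitis VAS (SAP 8.3.1.3), which no window table names.

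**3. Visits after EOT.** Last planned dose is Day 85. Days since last dose = study day − 85, shown without / with a +1 convention, then read in Table 2a.

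| Study day | Days since last dose | Last-dose clock | First-dose clock |
|---|---|---|---|
| 114 | 29 / 30 | Week 4 | Week 16 |
| 141 | 56 / 57 | Week 8 | Week 24/EOS/ETV |
| 169 | 84 / 85 | Week 12 | Week 24/EOS/ETV |

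(In Table 2d, Day 141 on the first-dose clock is Week 20.)

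- Every day from 114 to 174 maps to Week 4, 8 or 12.
- To reach the Table 2a Week 24 window (127–182), a visit must fall on Day 85 + 127 = 212, or Day 211 with +1. The latest scheduled end-of-study day is 169 + 5 = 174.
- Over Days 114–182 (69 days, no +1), the number of days keeping their first-dose label is 0 for a last dose on Day 85 or Day 57, 27 for Day 29, and 68 for Day 1.

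**The case against.** **Period dates.** The sections that use the term already settle it. The window tables, SAP 8.1.1 and 8.1.2, and the model time points all include Week 16, and Table 2e gives Lund-Mackay its own Week 16/EOT window (Days 85–126). Sixteen weeks from Day 1 is also exactly Days 1–112, so the table is arguably consistent with a strict 16-week count. The adverse-event mismatch covers one calendar day. This shows that the intent is clear and that a real loss of Week 16 co-primary data is unlikely. It does not make the date rule right: SAP 3.4 and Protocol 4.1 both count the Day 113 visit as a treatment-period visit, and SAP 8 names the period without exception.

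**Table 2f.** It affects exploratory diary data only. Nocturnal awakenings are descriptive, and the seven-day shift is the same in every arm, so no bias between arms is shown. That limits the consequence, but the printed mid-week targets confirm that the windows themselves are mislabelled.

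**Visits after EOT.** Days 141 and 169 are scheduled visit days, and scheduled visits keep their eCRF label. Only unscheduled and ET visits after EOT move, and a moved record is analysed at the earlier visit only when that window has no scheduled record. The documents give no frequency. All of this stands as a limit on reach, but the mapping is still wrong for any unscheduled or ET visit on those days. A separate last-dose table would be another coherent remedy, but the plan contains none.

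**Conclusion.** The concern holds on all three counts.

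- **Period dates:** a contradiction at the visit carrying both co-primary endpoints. The boundary is one day off at target dates, and the intent is recoverable from other sections.
- **Table 2f:** wrong as printed, by a constant seven days from Week 16 onward. It changes the exploratory Week 16 NPIF comparison, and the weekly rhinosinusitis VAS if the table is meant for that scale. The co-primary endpoints use Table 2a and are not touched.
- **Visits after EOT:** wrong by design for late last doses, but confined to a small class of records that the documents do not let us count.

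The day counts assume doses and visits on target dates, except where the ±5-day range is shown. This should be fixed before unblinding. It does not threaten the primary analysis if the evident intent is followed.

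**What to change.** - **SAP 6.2.3:** end the Treatment Period on the Visit 7/EOT date, inclusive, for efficacy, and start Safety Follow-up the next day. At target dates this agrees with SAP 10.2.
- **Table 2f:** set Week 16 to Days 106–112 (target 109), Week 20 to 134–140 (137) and Week 24 to 162–168 (165), and print the rows for Weeks 5 to 15.
- **SAP 6.4 and Table 2f:** replace the EQ-VAS with the weekly rhinosinusitis VAS, and leave the EQ-VAS under QoL in Table 2a.
- **SAP 6.4:** delete the last-dose sentence and map all unscheduled and ET visits by study day from first dose. This follows the section's own opening rule and the tables' target days.

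The cost is SAP wording and table edits, with matching programming specifications. No new data are needed, and sample size, power and alpha do not change.

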6.3. Missing Data

6.3.1. Birth Dates

Birth date may not be needed, if the age is provided. However, in case the birth date is needed for calculation, if the date of birth is only partially available, the first of the month will be imputed for any missing days and January will be imputed for any missing months. Imputed dates will not be presented in the data listings.

